### 4. EXECUTION

#### 4.1 Patient recruitment

Patients who received the multifocal lens LS-313 MF30 in Neubrandenburg at one or both eyes will be asked to participate in this observational study.

#### 4.2 Insurance

A patient and travel insurance is taken out before the start of the study.

#### 4.3 Patient identification

After completion of the data collection, each record will be encrypted.

#### 4.4 Documentation

A data collection form (attachment) is used. The following intraoperative information is collected retrospectively from the electronic patient file of the Dietrich-Bonhoeffer-Klinikum:

- Name and address of the patient
- Date of Birth
- Date of surgery
- Surgeon
- Operated eye (OD/OS)
- Performed cataract surgery with or without femtosecond laser
- Refractive power of the MICS IOL

The following postoperative information will be collected prospectively within the examination date, for the respective patient's eyes treated with the LS-313 MF30 Multifocal Lens:

- postoperative objective refraction values using auto-refractors in miosis
- postoperative objective refraction values using the PR 50 and 60 (Rodenstock, Munich)
- postoperative objective refraction values using the KR-1W (TOPCON, Willich, Germany)
- postoperative objective refraction values, pupillometry, topography and aberrometry with the iTrace in miosis and mydriasis (Tracey Technologies, Houston, Texas, USA)
- postoperative subjective refraction values with and without correction for the determination of the far and near vision
- pupil width in miosis and mydriasis
- corneal condition
- Assessment of vision impairment by the anterior capsule
- Centering of the intraocular lens
- IOL axis according to TABO scheme
- Assessment of the clarity of fundus insight

A data collection sheet serves as documentation and will be transferred into the Excel database (version 14.0.7166.5000/32-Bit, Microsoft, USA) by the study assistants.

#### 4.5 Study investigations

The study will collect the data as follows:

##### 4.5.1 Ophthalmological history

Available data of the general and ophthalmological anamnesis are collected from the existing patient record. This includes general and ophthalmic medication, past medical conditions, past operations, the surgery date, operated eye, pre-op IOL master, surgeon, femto laser if used and refractive power, type and manufacturer of implanted intraocular lenses.

##### 4.5.2 Uncorrected distance and near vision

- ETDRS panel / Snellen panel CAT. NO. 2110 (Precision Vision, Illinois, USA) is used for uncorrected distance vision evaluation. A reading chart is used to test uncorrected reading vision.

##### 4.5.3 Best corrected visual acuity for distance

- ETDRS panel / Snellen panel CAT. NO. 2110 (Precision Vision, Illinois, USA): ) is used for corrected distance vision evaluation. A reading chart is used to test corrected reading vision.  
A trial frame is used to determine

##### 4.5.4 Refraction determination in miosis using autorefractometers

- a) Refractometer/Keratometer, Mod.ARK-760A (NIDEK CO.,LTD, Gamagōri, Japan)  
(Location: Cataract center, room B.5.49)

Refraction values will be measured automatically.

- b) Auto Kerato Refractometer KR-800s (TOPCON, Willich, Deutschland).  
(Location: Functional diagnostics, room B.5.45/46):

Refraction values will be measured automatically. In addition, pupil size will be recorded.

- c) Autorefractometer ARK-560A (NIDEK CO,LTD, Gamagōri, Japan)  
(Location: Ambulance, room B.6.33.1)

Refraction values will be measured automatically.

##### 4.5.5 Refraction determination in miosis using combined Kerato- and Aberrometer KR-1W (TOPCON, Willich, Germany) (Location: Functional diagnostics, room B.5.45/46)

Refraction and pupil size will be measured automatically.

#### 4.5.6 Refraction determination in miosis using Purkinje reflex and different optical WF measurement zones of the iTrace device (Tracey Technologies, Houston, Texas, USA)

The room lighting is darkened and the window blinds closed. The patient is positioned with the chin on the chin rest and the forehead on the forehead rest. Afterwards, the patient's head is turned slightly sideways so that the iTrace measuring head can be moved towards the patient's eye. The eye not to be examined is first covered with an occluder which the patient himself holds in his hand. The patient is asked to look through the iTrace device and fix a distant object. It is important to ensure that nothing blocks the patient's gaze, as this affects the patient's accommodation and may result in unwanted refractive readings.

Now select the single red wavefront icon (manual measurement) in the upper right corner of the screen to start a WF scan. The white target is first positioned on the edge of the entrance pupil, outside the center. At the same time, the iTrace device is moved back and forth to focus the iris details and thus set the most suitable measurement level. The 4 white dots (4 IR points) in the center of the pupil represent the Purkinje reflexes that are used to center the following measurements (center of 4 points). The patient is asked to focus the red light. Now the assistant presses the Enter key to make the red scan points visible. For the first measurement the separate 1 mm scan button (64 points) is selected. The scan pattern is centered on the center of the 4 white dots (Purkinje reflexes). The patient is asked not to move, to blink twice and then open both eyes wide. The fixation light is switched off with F10. Pressing the button on the joystick triggers the measuring process. If all wavefront measurement points are validly evaluable (visible within the pupil), the measurement is saved by confirming the green check mark symbol. Otherwise, the measurement has to be repeated until a valid evaluation is possible.

For the 2nd, 3rd and 4th measurement, the red wavefront symbol is selected again, followed by the Enter key and selecting 2, 3 or 4 in the keypad to move the measurement zone to 2, 3 or 4 mm. At the same time, the iTrace measuring module is held firmly in place with one hand and moved only slightly backwards to remain in the measuring plane. The respective measuring processes for the 2, 3 and 4 mm measuring zones are carried out analogously to the procedure described above for 1 mm measurement, checked for validity and saved.

The data collection for the 4 measurement zones is carried out using the WF Verification Display by selecting the respective WF measurement individually in the patient main menu and confirming with the blue arrow pointing to the right. The refraction value (Sph, Cyl and Axis) is shown in the WF verification display. Furthermore, the SE spot in the RSD (Retinal Spot Diagram) is set as distortion-free as possible by pressing the F1 and F2 keys to determine the focus of the Spherical Equivalent. Care must be taken to ensure that the outermost color ring is used for the evaluation, which ensures a symmetrical setting (orientation rather to the green ring). The indicated defocus value corresponds to the opposite numerical value of the refraction, therefore plus values must be raised with minus values and minus values must be raised with plus values.

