## 1. BACKGROUND

Since 2012, the asymmetric multifocal posterior chamber lens MICS LS-313 MF30 (Oculentis GmbH, Berlin, Germany) has been implanted in the Department of Ophthalmology Neubrandenburg following cataract surgery in suitable patients.

To determine the refraction after the implantation of an asymmetric multifocal intraocular lens we have used the eye refractometer PR 60 or PR 50 (Rodenstock, Munich). This manual refractometer projects test mark images onto the retina of the eye via a measuring beam path, which are viewed via a coaxial observation beam path and are manually focused.

So far, this is our only objective way to measure the different focal points of the multifocal lens.

Furthermore, we have the opportunity to determine the distance and near refraction subjectively. The accuracy of this method, however, depends on the cooperation of the patient.

The manual eye refractometers PR 60 and PR 50 (Rodenstock, Munich) work with light cones of 3 mm diameter.

The optic of the LS-313 MF30 intraocular lens has a diameter of 6 mm, half of the optic is used for far vision, half for near vision. Under ideal conditions (pupil becomes maximally dilated; no peripheral capsule opacity or secondary cataract cover the peripheral part of the optic) the Rodenstock refractometer provides a sharp image on the fundus.

However, usually it is not possible to image the entire light cone of the Rodenstock refractometer on the retina in case of a non-maximally dilated pupil, a peripheral secondary cataract or a peripheral capsule opacification or an anterior capsular phimosis. Therefore, sometimes the separate determination of the axial refraction for the near and the far part is not sufficiently accurate.

The new iTrace device (Tracey Technologies, Houston, Texas, USA) could provide more accurate measurement results. This wavefront device uses significantly smaller cones of light (about 1mm) that should allow you to determine more accurate readings in multifocal optics.

A reliable objective refraction is required if patients fail to achieve sufficient visual acuity after the implantation of a multifocal IOL.

This study will investigate whether the new iTrace device (Tracey Technologies, Houston, Texas, USA) is suitable for precisely measuring the far and near part of the LS-313 MF30 Intraocular Lens.

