### 2.2 Study population

- 100 eyes should be included in the study

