## 5. STATISTICAL EVALUATION

The data to be documented are transferred from the electronic patient record and the data collection sheet into an Excel spreadsheet by the study assistants. The patient's name, first name, date of birth, and address are not transferred. The personal data will be replaced by a serial number. Due to this serial number, it can no longer be associated with any particular individual.

The data is then transferred to the program STATISTICA (StatSoft, Inc., Hamburg, Germany) and evaluated.

Main question: Which of the refraction measurement methods allows an accurate and reproducible refraction determination after implantation of a multi-focal intraocular lens LS-313 MF30? The reference method is the determination of the subjective refraction.

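### Do the undilated 3 and 4 mm iTrace zones bias the comparison of methods because only larger pupils can yield a valid scan?

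*Protocol*

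**What the plan says.** Section 4.5.6 of the protocol describes iTrace refraction before dilation, in a darkened room, with the scan pattern centred on the Purkinje reflexes. The rule for keeping a scan is "If all wavefront measurement points are validly evaluable (visible within the pupil), the measurement is saved". For any other scan the instruction is "Otherwise, the measurement has to be repeated until a valid evaluation is possible". It is written for the 1 mm zone and then extended, since the "processes for the 2, 3 and 4 mm measuring zones are carried out analogously to the procedure described above for 1 mm measurement". Sphere, cylinder and axis are taken from each zone: "The refraction value (Sph, Cyl and Axis) is shown in the WF verification display".

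Sections 4.5.8 and 4.5.9 draw the iTrace pupil size, the kappa and alpha angles and the higher-order aberrations from the 3 mm scan. The inclusion and exclusion criteria do not mention pupil size. For the KR-1W, section 4.5.5 says only "Refraction and pupil size will be measured automatically", and section 4.5.4 is similarly brief on the autorefractors. The target in section 2.2 is "100 eyes should be included in the study".

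Section 5 asks "Which of the refraction measurement methods allows an accurate and reproducible refraction determination", with subjective refraction as the reference. It names no analysis set and no rule for comparing one method with another.

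**The concern.** A 4 mm pattern does not fit in a 3.5 mm pupil, however often the scan is repeated. Read literally, the repeat instruction has no end in such an eye, and the section gives neither a stopping point nor a missing-value entry. Operators might leave the zone out, move the pattern off the Purkinje centre or save an incomplete scan, and these give different data.

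If the rule is kept, values are missing according to pupil size. That could matter with this lens, because "half of the optic is used for far vision, half for near vision": the share of each half exposed may depend on the pupil, and so may the gap between an objective reading and subjective refraction. A 4 mm result from larger-pupil eyes, set beside a 1 mm or autorefractor result from all eyes, could then show a difference between eyes and be read as a difference between methods. The 3 mm aberrations and the kappa and alpha angles would be missing in some of the same eyes.

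**Working it through.** The protocol has no figure of its own to reproduce: the 100 eyes come without a derivation and no pupil distribution is given. The check has two parts.

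**1. What the text leaves open.** Take the three things an operator might do when the pupil is too small.

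- Move the pattern: not allowed, since section 4.5.6 fixes the centre on the Purkinje reflexes.
- Save an incomplete scan: not allowed, since all points must be evaluable.
- Leave the zone without a saved scan: the only outcome that breaks neither rule.

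The gap is therefore the entry to make for that outcome. Section 4.4 names a data collection form as an attachment, which is a natural place for it, but the form is not shown.

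**2. How large the effect could be.** All inputs except the zone widths and the 100 eyes are assumptions: normal pupil diameter with mean m of 3.5 to 5.5 mm and SD s of 0.7 or 0.9 mm, offset d of 0 to 0.3 mm between Purkinje centre and pupil centre, and a slope b of 0.1 to 0.3 D in the error against subjective refraction per mm of pupil.

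- Smallest usable pupil: t = zone + 2d. This gives 3.0 to 3.6 mm for the 3 mm zone and 4.0 to 4.6 mm for the 4 mm zone.
- Share of eyes without a scan: Φ((t − m)/s).
- Rise in mean pupil among eyes with a 4 mm scan, at d = 0: s·φ(a)/(1 − Φ(a)), with a = (4 − m)/s.
- Spurious difference, 4 mm zone in available eyes against 1 mm zone in all eyes: b × that rise.

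Example at m = 4.0, d = 0: a = 0, so half of the eyes lack a 4 mm scan. The rise is 0.7 × 0.3989/0.5 = 0.56 mm, or 0.72 mm with s = 0.9. The spurious difference runs from 0.1 × 0.56 = 0.06 D to 0.3 × 0.72 = 0.22 D.

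| Assumed mean pupil (mm) | Eyes per 100 without 3 mm scan | Eyes per 100 without 4 mm scan | Rise in mean pupil, 4 mm (mm) | Spurious difference, 4 mm (D) |
|---|---|---|---|---|
| 3.5 | 24–56 | 71–94 | 0.91–1.06 | 0.09–0.32 |
| 4.0 | 8–33 | 50–80 | 0.56–0.72 | 0.06–0.22 |
| 4.5 | 2–16 | 24–56 | 0.28–0.43 | 0.03–0.13 |
| 5.0 | 0–6 | 8–33 | 0.11–0.22 | 0.01–0.07 |
| 5.5 | 0–2 | 2–16 | 0.03–0.09 | 0.00–0.03 |

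Now compare the zones within one eye. Write the error at zone z as b × pupil + noise. In the difference between the 4 mm and the 1 mm error of the same eye, b × pupil cancels, so the expected spurious difference is 0 whatever b, m and s are. The price is precision: with 50 of 100 eyes the confidence interval is √(100/50) = 1.41 times as wide.

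**The case for a change.** The best argument for a change is that this is an acquisition instruction, and no analysis plan can recover what was done at the device. The protocol shows elsewhere that it can write such rules: section 4.5.10 stops the dilated autorefractor test when 5 to 10 readings scatter too much, and section 4.5.12 requires the whole decentred 1 mm pattern to lie within the pupil. One sentence in section 4.5.6 would cost nothing and would give every operator the same ending.

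Part of this stands. The repeat instruction is open-ended, and an explicit entry for a zone wider than the pupil would be tidier. But most of such a sentence would restate the centring and completeness rules already there, and the same small-pupil eyes would still have no wide-zone value, because the limit is geometric.

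The bias argument is weaker. Each iTrace error is already paired with subjective refraction in the same eye. Which eyes enter a comparison between zones or devices is commonly settled in an analysis plan, and one may exist here. The contrast with the other devices rests on silence: a reading taken automatically is not shown to succeed in every small pupil.

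**Conclusion.** No change to the plan follows. The observation is correct: where the undilated pupil is smaller than the zone, allowing for any offset, section 4.5.6 cannot be satisfied and does not say how to close the attempt. This is missing detail that operators and analysts would fill sensibly, by recording no scan for that zone, stating how many eyes contributed to each zone, and comparing zones or devices in eyes that have both values.

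The harm needs three things together: a material share of pupils below 3 or 4 mm, an error that changes with pupil size, and an analyst who compares different eyes. The document establishes none of them. The loss of 0 to 94 eyes per 100 (across both zones) and the 0.00 to 0.32 D rest on assumed pupil and slope values, and the darkened room favours the smaller end. The KR-800s and KR-1W also record pupil size, so any selection can be described. The measurements most central to the Background's aim, the far and near parts of the lens, use 1 mm scans in dilated pupils and are not touched by this point.

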#### 4.5.7 Determination of Corneal Topography in Miosis using the iTrace (Tracey Technologies, Houston, Texas, USA)

Immediately after the wavefront measurements, 3 topographic images are taken. Therefore, a bright illumination light is projected onto the patient's cornea by the device. Now the single circular blue topography icon (manual measurement) in the upper right corner of the screen is selected to start a CT scan.

By means of the joystick, the green, central Placido circle will be positioned in the middle of the yellow quadrangular target by horizontal and vertical adjustment.

The picture is accurately centered when the dark green ring turns light green. It should be noted that the laser focus is always situated at the right side of the yellow square target.. The iTrace device is now moved slowly towards the patient until the white laser focus point crosses the center of the green ring and the yellow target. During the approach, the software will automatically start to track the laser focus point (a red cross will appear). The iTrace device will then automatically take the measurement when the bright green ring and the yellow target are exactly centered and the white laser focus points move slowly through the bright green circle. The CT-Verification Display, which is now automatically displayed, checks whether the measurement is valid (uniformly visible Placido circles and no eyelids in the measurement area). Afterwards the valid measurement is saved by pressing the green tick. A total of 3 valid measurements are collected and saved. Using the Compare function, the 3 measurements are qualitatively compared with each other and the recording with the smallest deviations marked with an \* asterisk in the note field.

The topography image with the \* asterisk is individually evaluated, without selecting a WF measurement, using the CT-Verification Display (in the patient's main menu, the right-pointing blue arrow) and the SIM-K values K1 and K2 as well as the flat corneal axis by K1 are collected.

#### 4.5.8 Determination of pupillometry in Miosis using the iTrace (TraceyTechnologies, Houston, Texas, USA)

The pupillometry is obtained from the performed WF and CT scans. Therefore, the WF image with 3 mm measurement zone and the specified CT image with the \* asterisk are selected simultaneously in the main patient menu. Angle K/A (Cataract Evaluation menu) displays the pupil size and decentence distance, as well as the axis of the Kappa angle and Alpha angle.

#### 4.5.9 Determination of HOA (Higher Order Aberrations) in Miosis using the iTrace (TraceyTechnologies, Houston, Texas, USA)

The evaluation of Higher Order Aberrations (HOA) is also recorded with the WF image of the 3 mm measurement zone and the simultaneously selected CT measurement with \* asterisks. The right-pointing blue arrow in the main patient menu has to be clicked on, which opens the WF and CT Summary Display. Chang Analysis is selected subsequently and by clicking the right mouse button and selecting the combined display the individual displays of the total, internal and corneal aberrations are opened. For the total eye, internal (calculated value of the implanted IOL) and cornea, the displayed aberration value for HO Total, Spherical Aberration and Astigmatism is documented respectively.

For all further examinations, the pupils are artificially dilated with neosynephrine-POS 10% eye drops and Mydrum eye drops.

#### 4.5.10 Visus determination in Mydriasis using Autorefractometers:

For all three autorefractometers, following the standard miosis measurement, it is tested whether reliable refraction readings can be obtained for the far and near parts of the IOL by focusing on the lense's upper and lower halves of the dilated pupil.

20 to 30 minutes after drug dilatation of the pupils (depending on the reaction of the patient's eye), the procedures listed under 4.5.4.a, b and c are repeated. By contrast, this measurement should initially focus on the upper half of the lens, as far as possible. When the device has triggered and the measured values have been

collected, the data is transferred to the electronic patient record in FIDUS and saved. Subsequently, the process for the lower part of the lens is repeated.

If values scatter too high in 5 to 10 measurements this test procedure is completely stopped and carried on with point 4.5.6.

Pupil width in mydriasis is carried out with the Auto Kerato Refractometer KR-800s (TOPCON, Willich, Germany). This is achieved by pressing the "corneal diameter" button (description under 4.5.4.b). A measurement window with two positioning bars appears. Moving the bars to the right and left of the eye using the displayed control keys will display the width of the pupil.

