#### 4.5.11 Determination of the focal point in the far and near part of the intraocular lens in Mydriasis using the eye refractometer PR60 or PR50 (Rodenstock, Munich)

(Location: PR50 Cataract center, room B.5.50, Ambulance, room B.6.31+32  
PR60 Ambulance, room B.6.35)

The doctor ensures that the scale of the observer eyepiece is set to 0, or that his own ametropia is correctly taken into account. It is important that the patient's pupils are sufficiently dilated, since the visible annular illumination zone must be placed completely or at least for the most part in the patient's pupil plane. The doctor looks at the test mark images on the retina on the observation beam path and focuses them. The measured value is then read from a scale in diopters. This measuring process is carried out for the far part as well as for the near part of the IOL. For this purpose, the investigator tries to irradiate most of the annular illumination beam path through the far or near part of the IOL.

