#### 4.5.12 Determination of the focal point in the far and near part of the intraocular lens in Mydriasis using the iTrace (TraceyTechnologies, Houston, Texas, USA)

(Location: functional diagnostics)

The room lighting is darkened and the window blinds closed. The patient is positioned with the chin on the chin and forehead on the appropriate rests. Afterwards, the patient's head is turned slightly sideways so that the iTrace measuring head can be moved towards the patient's eye. The patient is asked to look through the iTrace and focus on a distant object. It is important to ensure that nothing blocks the patient's gaze, as this affects the patient's accommodation and may result in unwanted refractive readings.

The following measurements are taken in manual mode by selecting the single red wavefront icon in the upper right corner of the screen. The white target is first positioned on the edge of the entrance pupil, outside the center. At the same time, the iTrace is moved back and forth to focus on the iris details and thus set the most suitable measurement plane. The patient is asked to focus on the red light. Pressing the Enter key makes the red scan points visible. For the following measurements the separate 1 mm scan button (64 points) is selected. The scan pattern is centered on the optic center of the implanted multifocal lens. It is important to ensure that the scan pattern is located exactly between the two lens markings of the optics. The patient is asked not to move, to blink twice and then open both eyes wide. The fixation light is switched off with F10. Pressing the button on the joystick triggers the measuring process. If the wavefront measurement points are validly evaluable (visible within the pupil), the measurement is confirmed and saved by selecting the green check mark symbol. Otherwise, the measurement is repeated until a valid evaluation is possible.

Subsequently, a decentered measurement is carried out, 1.5 mm away from the optical center of the multifocal lens in the IOL far and near part, respectively. It is decentered at right angles to the apparent IOL markers and the 1 mm scan pattern is moved from the IOL center 1.5 mm (estimated based on the presented

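### After the drops the PR is laid out before the iTrace, with no balancing of order and no recorded time, so a time or order effect cannot be separated from a device difference

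*Protocol*

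**What the plan says.** Protocol 4.5 introduces the investigations with "The study will collect the data as follows" and numbers them 4.5.1 to 4.5.14. Dilation begins at the end of 4.5.9: "For all further examinations, the pupils are artificially dilated with neosynephrine-POS 10% eye drops and Mydrum eye drops".

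- **4.5.10, autorefractors.** The three devices are used again: "20 to 30 minutes after drug dilatation of the pupils (depending on the reaction of the patient's eye), the procedures listed under 4.5.4.a, b and" (the sentence ends by having all three repeated). This is the only interval stated for a dilated measurement. The section also says "Pupil width in mydriasis is carried out with the Auto Kerato Refractometer KR-800s (TOPCON, Willich, Germany"), and it carries a stop rule: "If values scatter too high in 5 to 10 measurements this test procedure is completely stopped and carried on with point 4.5.6".
- **4.5.11, PR.** "It is important that the patient's pupils are sufficiently dilated, since the visible annular illumination zone must be placed completely or at least for the" greater part in the pupil plane. No minimum in millimetres, time since the drops or room lighting is given.
- **4.5.12, iTrace.** "The room lighting is darkened and the window blinds closed". A 1 mm pattern is read at the lens centre and 1.5 mm into each part, from wavefront scans opened without a topography scan. No time since the drops is given.

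Protocol 4.4 lists, among the data to be collected, pupil width in both states and iTrace pupillometry in both states. Section 5 asks which method is accurate and reproducible, with subjective refraction as the reference.

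**The concern.** Section 1 explains that the PR struggles when the pupil is not maximally dilated, and that the iTrace may do better because its light cones are smaller. The two devices therefore differ in how much they depend on the pupil, and the pupil may change with time since the drops. Followed as numbered, the protocol has the PR read earlier and the iTrace later in each eye.

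If the pupil were still widening, the PR would be read through a smaller pupil than the one the iTrace meets, and part of the difference would be credited to the iTrace. If dilation were receding, or fixation worsened over a long session, the later device would be at the disadvantage. Neither effect shrinks with more eyes. At stake is the comparison of the far- and near-part readings, for which Section 1 describes the PR as the department's only objective method so far.

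**Working it through.** The protocol states no figure on this point, so there is none to reproduce. Three checks apply.

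**1. What one order can estimate.** Let p1 and p2 be the mean PR reading in the first and second slot after the autorefractors, and t1 and t2 the same for the iTrace.

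- Order as numbered: the data estimate p1 − t2 only.
- Reverse order: the data estimate p2 − t1.
- Equal mix of both: the average is (p1 + p2)/2 − (t1 + t2)/2, the device difference at the same average position.

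From p1 − t2 alone, neither p1 − t1 nor p2 − t2 can be recovered at any sample size. Measuring against subjective refraction S does not help, because (PR − S) − (iTrace − S) = PR − iTrace. The order effect passes straight into the comparison of mean errors.

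For scale, the 95% half-width of a mean paired difference is 1.96 × SD/√n. With n = 100 eyes treated as independent and an assumed SD of 0.25, 0.50 or 0.75 D, it is 0.049, 0.098 or 0.147 D. A systematic offset of that size would not average out. The protocol gives no SD.

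**2. How differently the devices depend on the pupil.** Inputs are the PR cone of 3 mm and the optic of 6 mm, half far and half near (Section 1), and the iTrace pattern of 1 mm placed 1.5 mm off centre (4.5.12). Assumptions are a concentric pupil and lens, no magnification and a uniform disc for the PR beam.

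- PR: the largest circle inside a half-disc of radius R has diameter R, so a 3 mm cone needs R = 3 mm, a pupil of 6.0 mm.
- iTrace: the outer edge lies at 1.5 + 0.5 = 2.0 mm, a pupil of 4.0 mm.

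Below 6 mm the PR beam can be handled in two ways.

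(a) Kept wholly inside the pupil, it spills into the wrong half. With r = 1.5 and d = R − 1.5, the share is [r² arccos(d/r) − d√(r² − d²)]/(πr²). At 5.0 mm, d = 1.0, giving (2.25 × 0.8411 − 1.118)/7.069 = 0.774/7.069 = 11.0%.

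(b) Held 1.5 mm off centre, it is clipped by the iris. The share remaining inside is the two-circle overlap with d = r = 1.5, divided by πr². At 5.0 mm this is (2.25 × 1.970 + 6.25 × 0.5857 − 2.073)/7.069 = 6.02/7.069 = 85.2%.

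| Pupil (mm) | PR light in wrong half (a) | PR cone inside pupil (b) | iTrace pattern inside pupil |
|---|---|---|---|
| 4.5 | 19.6% | 74.2% | 100% |
| 5.0 | 11.0% | 85.2% | 100% |
| 5.5 | 4.0% | 94.5% | 100% |
| 6.0 | 0% | 100% | 100% |

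The change in pupil between the two steps has to be assumed. Growth from 5.0 to 5.5 mm would lower the PR's wrong-half share by 11.0 − 4.0 = 7.0 points; shrinkage over the same span would raise it by 7.0. With no change, or with pupils of 6 mm or more throughout, the figure is 0. The iTrace is unaffected in all of these cases. These are areas, not dioptres, and the protocol offers no way to convert them.

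**3. Whether pupil width is available at each reading.**

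- 4.4 lists iTrace pupillometry in mydriasis.
- 4.5.8 describes pupillometry for miosis only, from a 3 mm wavefront scan combined with a topography scan.
- 4.5.10 describes the dilated pupil width on the KR-800s, before the PR and iTrace in the numbering.
- 4.5.12 uses 1 mm scans without topography and describes no pupil read-out. 4.5.11 describes none either.

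The listed item thus has no described procedure, and no pupil width is tied to the PR reading.

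**The case against.** The strongest reply is that no sentence requires the PR before the iTrace. The lead-in to 4.5 covers everything, including history-taking, and where sequence matters the protocol usually says so, as in 4.5.7, 4.5.9 and 4.5.10; no such word links 4.5.11 to 4.5.12. The stop rule also departs from a single path. This stands: the order is the natural reading of the layout, not an explicit rule. It does not remove the problem, because an unstated order is not a balanced one. Read literally, the stop rule would send the eyes with the most scatter to an iTrace step next, so that order would depend on how hard the eye is to measure.

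Secondly, the wait is adapted to the eye, the PR also follows the autorefractors, and 4.5.11 asks for sufficient dilation. This stands too, and any effect may be small. But sufficiency has no threshold and partial placement in the pupil is accepted.

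Thirdly, the geometry uses a uniform disc, whereas 4.5.11 describes an annular beam that the examiner steers. The table therefore supports the ordering of the devices by pupil dependence, not the amount of any error.

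A reader might go further and infer that pupil width is taken only once, or that PR against iTrace is the main comparison. The protocol supports neither: 4.4 lists iTrace pupillometry in mydriasis, and Section 5 names subjective refraction as the reference, with the PR one of several comparators.

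**Conclusion.** The point holds as one of non-separability. As laid out, the PR precedes the iTrace after the drops, the order is not balanced and no time since the drops is recorded for either. The PR is the more pupil-dependent device: about 6 mm against about 4 mm, assuming a centred pupil and lens. Effects of elapsed time or fatigue cannot then be told apart from a device difference in the far- and near-part readings, and this bears on the ranking of methods. Room darkening, instructed for the iTrace only, adds a further difference between the two conditions.

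It would be tempting to conclude that the comparison is biased in favour of the iTrace. The documents do not show that: they give no pupil sizes, dilation time course or interval between the two devices, and the direction could be either. Separately, 4.4, 4.5.8, 4.5.10 and 4.5.12 must be reconciled on dilated pupillometry, and the reference in 4.5.10 to 4.5.6, an iTrace step in miosis, must be reconciled with an eye that is already dilated. The dilation regimen itself is not judged here.

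**What to change.** - Alternate 4.5.11 and 4.5.12 by enrolment order, entered on the data collection form at the visit (odd: PR first; even: iTrace first), with both eyes of a patient in the same order. Enrolment order is safer than the serial number, which Section 5 introduces at transfer to Excel and which may not exist at the examination.
- Record the clock time of the drops and of each PR and iTrace reading.
- Take the existing KR-800s pupil width directly before this pair. It remains an approximation to the pupil at each reading.
- State the room lighting for 4.5.11. Alternation balances time and fatigue but leaves lighting tied to the device.
- Reconcile 4.4, 4.5.8, 4.5.10 and 4.5.12 on dilated iTrace pupillometry, either by describing the procedure or by removing the item, and reconcile the stop-rule reference to 4.5.6 with the dilated state.

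The cost is a few protocol sentences and three time fields, with no added measurement for the alternation. The PR and the iTrace stand in different rooms, so about half the patients would walk somewhat more.
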